CARTISTEM® PHASE I/IIa CLINICAL TRIAL PROTOCOL MP-0201-01

Version 3.2 Date: 15 March, 2017

CARTISTEM® PHASE I/IIa CLINICAL TRIAL PROTOCOL

CARTISTEM®

page 1 of 137

CONFIDENTIAL: These all contents herein are the sole property of MEDIPOST Co., Ltd. Any reproduction or distribution of this document without the written consent of MEDIPOST Co., Ltd is prohibited. Copyright © 2017 MEDIPOST Co., Ltd.

Name of Company Name of Product: Umbilical Cord Blo Ex vivo, Combined	Protocol #: MP-0201-01								
Protocol Title	Evaluation of Safety and Exploratory Efficacy of CARTISTEM [®] , a Cell Therapy Product for Articular Cartilage Defects: A Phase I/IIa Clinical Trial in Patients with Focal, Full-thickness Grade 3-4 Articular Cartilage Defects of the Knee								
Clinical Phase	Phase I/IIa								
Study Overview	dy Overview CARTISTEM [®] will be administered at doses ranging from 0.5×10 ⁷ to 2.25×10 ⁷ hUCB-MSC (0.25×10 ⁷ cells/cm ² ; 0.5 mL/cm ² with 0.5×10 ⁷ MSC/mL) to patients with focal, full-thickness, Grade 3-4 articular cartilage defects of ≥ 2cm ² in size. Safety: Patient safety will be assessed step-wise with increasing levels of total hUCB-MSC and HA exposure: a total of 12 patients will be enrolled and treated with CARTISTEM [®] to evaluate whether dose limiting toxicity (DLT) is detected. DLT is defined as toxicity or adverse event of Grade 3 or higher [80 points or higher for pain] in two or more events at the surgery site among swelling, tenderness, range of motion, and pain in any one visit. DLT is also defined as adverse drug reaction of Grade 3 or higher in the Common Toxicity Criteria Adverse Events (CTCAE), Version 4.0, with the exception of the following events and that they are unresolved for 7 consecutive days, despite medical interventions: ✓ Abnormal results in lab test (Acidosis, Hyponatremia, Hyperbilirubinemia, etc.) ✓ Abnormal results in lab test (Acidosis, Hyponatremia, Hyperbilirubinemia, etc.) ✓ Pain, defined as severe pain; limiting self-care ADL ✓ Pain, defined as severe pain; limiting self-care ADL								
	✓ Fever, defined as > 40.0 degrees C (> 104.0 d	degrees F) for > 24 hours							
	Initially, 6 patients with lesion sizes of 2-5 cm ² w (Dosage A); if dose limiting toxicity is not detect after administration, an additional 6 patients, with	ed during a 12 week period							

page 2 of 137

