The primary objective of the proposed single-center phase I/IIa study is to evaluate the safety of CARTISTEM[®], an allogeneic-unrelated mesenchymal stem cell (hUCB-MSC) suspension mixed with sodium hyaluronate, at doses ranging from 0.5×10^7 to 2.25×10^7 hUCB-MSC in patients with articular cartilage defects that are equal or greater than 2cm².

The secondary objective of the study is to evaluate the efficacy (regeneration of defective cartilage and decrease of pain) of CARTISTEM[®].

CARTISTEM[®] will be administered, as a function of the defect size, at a cell density of 0.25×10^7 cells/cm² (0.5 mL/cm² with 0.5×10^7 hUCB-MSC/mL) directly into the articular cartilage defect by open surgery.

CARTISTEM®

page 18 of 137

CONFIDENTIAL: These all contents herein are the sole property of MEDIPOST Co., Ltd. Any reproduction or distribution of this document without the written consent of MEDIPOST Co., Ltd is prohibited. Copyright © 2017 MEDIPOST Co., Ltd.

A total of 12 patients, initially 6 patients with defect sizes of 2 to 5 cm² (Dosage A) followed by an additional 6 patients with defect sizes of above 5 cm² (Dosage B), will be enrolled sequentially in 2 groups in order to evaluate whether dose-limiting toxicity (DLT) is detected.

Each patient will undergo a 6-week screening period for eligibility and a 12-month follow-up observation period for both the primary (safety) and secondary (efficacy) endpoints of the study. There is an additional long term follow-up observation visit at 24 months. The estimated total duration of the study is approximately 24 months.

Prior to administration of CARTISTEM[®], the defect will undergo debridement, and following appropriate preparation, perforation of the subchondral plate.

CARTISTEM[®] is applied directly onto the entire defect site.

For use at the clinical site, CARTISTEM[®] will be provided as a cell suspension and lyophilized sodium hyaluronate in separate glass vials.

In terms of post-operative rehabilitation, patients will be started on a continuous passive motion (CPM) device on post-operative day 1 and refrain from high-impact activities such as running for 20 to 24 weeks.

6 Study Design

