6.2 Subject Selection Criteria

- 1) Inclusion Criteria
- A. Patients with an intended- to- treat single focal, full-thickness cartilage defect (ICRS [International Cartilage Repair Society] Grade 3 or 4) of the knee as a result of ageing,

CARTISTEM®

page 19 of 137

CONFIDENTIAL: These all contents herein are the sole property of MEDIPOST Co., Ltd. Any reproduction or distribution of this document without the written consent of MEDIPOST Co., Ltd is prohibited. Copyright © 2017 MEDIPOST Co., Ltd.

trauma, or degenerative diseases

- B. Age \geq 18 years old
- C. Size of the articular cartilage lesion is $\ge 2 \text{ cm}^2$
- D. Swelling, tenderness and active range of motion \leq Grade II
- E. Joint pain : 20-mm 60-mm on VAS (Visual Analog Scale) at the time of Screening
- F. Appropriate blood coagulation, kidney and liver function laboratory parameters:
 - ✓ PT(INR) < 1.5, APTT <1.5×control
 - ✓ Creatinine \leq 2.0 mg/dL, Albumin \leq trace in urine dipstick test
 - ✓ Bilirubin \leq 2.0 mg/dL, AST/ALT \leq 100 IU/L
- G. Ligament instability \leq Grade II
- H. Lower extremity alignment within 5 degrees of the neutral weight bearing axis
- I. No meniscal surgery within the past 3 months and more than 5mm of meniscal rim remaining
- J. Ability and willingness to fully participate in the post-operative rehabilitation program
- K. Subject is informed of the investigational nature of this study, voluntarily agrees to participate in the study, and signs an IRB-approved informed consent prior to performing any of the screening procedures
- L. Body Mass Index (BMI) \leq 35 kg/m²
- 2) Exclusion Criteria
- A. Patients that have been treated previously and are asymptomatic
- B. Avascular necrosis / osteonecrosis
- C. Autoimmune or inflammatory joint disease
- D. History of infection within the past 6 weeks
- E. Surgery or radiation therapy within the past 6 weeks
- F. Serious medical co-morbidities which would otherwise contraindicate surgery, as determined by the investigator
- G. Currently pregnant or nursing
- H. Psychotic diseases, epilepsy, or any history of such diseases

CARTISTEM®

page 20 of 137

CONFIDENTIAL: These all contents herein are the sole property of MEDIPOST Co., Ltd. Any reproduction or distribution of this document without the written consent of MEDIPOST Co., Ltd is prohibited. Copyright © 2017 MEDIPOST Co., Ltd.

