6.3 Number of Subjects

1) Estimated Number of Patients

This study requires 12-18 patients (6-9 patients per arm depending on rate of DLT) for two different dose ranges (Dosage A: defect sizes of 2-5 cm² and Dosage B: defect sizes of above 5 cm²).

2) Target Number of Subjects and Rationale

This is a phase I/IIa clinical trial to evaluate safety and exploratory efficacy of the investigational drug product. Therefore, it is not considered critical to base the number of subjects on formal statistical power calculations. Six patients at each dose cohort enrolled sequentially are considered sufficient for this study. This study will be performed with two dose ranges, on the basis of existing pre-clinical test results. Initially, 6 patients with defect sizes of 2-5 cm² will be enrolled in Dosage A. If no DLT is seen during Dosage A, another 6 patients with larger defect sizes (above 5 cm²) will be recruited for Dosage B of the study. There could be a need for an intermediate dose or up to 6 additional patients, based on the rate of DLT seen.

CARTISTEM®

page 21 of 137

CONFIDENTIAL: These all contents herein are the sole property of MEDIPOST Co., Ltd. Any reproduction or distribution of this document without the written consent of MEDIPOST Co., Ltd is prohibited. Copyright © 2017 MEDIPOST Co., Ltd.

1) Initial Administration Dosage and Rationale

It is somewhat well understood by developers and regulators of living cell therapies that for products like CARTISTEM[®] administered locally into an anatomical defect there is no simple extrapolation of a safe starting dose in humans based primarily upon body surface area calculations derived from animal studies.

In addition, dose determinations in this clinical setting should take into account the surface area of the cartilage defect such that all NOAEL values should be converted into a unit quantity (cells/cm²) at the application site. This approach applies to most therapeutics administered into anatomical compartments that have little subsequent distribution outside of the compartment; it is recommended that doses are normalized between species according to the compartmental volumes and amount of the therapeutic product.

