6.5 Dose Escalation

This clinical trial will employ the following dose escalation scheme:

[figure not shown]
A total of 12-18 patients will be enrolled and treated with CARTISTEM[®] for dose limiting toxicity (DLT) evaluation. Initially, 6 patients with lesion sizes of $2 - 5 \text{ cm}^2$ will be assigned to Dosage A and treated with $0.5 - 1.25 \times 10^7$ MSCs; if dose limiting toxicity is not observed at the 3 month time point for the first clinical efficacy evaluation, then another 6 patients with lesion sizes of above 5 cm² will be assigned to Dosage B and treated with more than 1.25 x 10^7 MSCs for further safety evaluation. If a DLT occurs to one or two patients of the group treated with the dosage A, 3 more patients will be assigned to dosage A. If DLT happens to 3 of the patients who were treated with the dosage A or above, this study will be halted and the FDA and IRB will be notified. The Independent Data Monitoring Committee will perform a comprehensive review of safety (see Section 9.1).

CARTISTEM®

page 24 of 137

CONFIDENTIAL: These all contents herein are the sole property of MEDIPOST Co., Ltd. Any reproduction or distribution of this document without the written consent of MEDIPOST Co., Ltd is prohibited. Copyright © 2017 MEDIPOST Co., Ltd.

If no DLT occurs to any of the dosage A patients, another 6 patients with larger defect sizes will be enrolled and assigned to dosage B. In case of no DLT observed, a total of 12 patients will be enrolled for safety and efficacy evaluation. However, 18 patients could be enrolled if DLT occurs to two patients. If DLT occur 3 or more patients treated with Dosage B, this study will be halted and the FDA and IRB will be notified. The Independent Data Monitoring Committee will perform a comprehensive review of safety (see Section 9.1).

CARTISTEM®

page 25 of 137

CONFIDENTIAL: These all contents herein are the sole property of MEDIPOST Co., Ltd. Any reproduction or distribution of this document without the written consent of MEDIPOST Co., Ltd is prohibited. Copyright © 2017 MEDIPOST Co., Ltd.

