6.6 Definition of Maximum Permissible Dose and Method of Dose Escalation

Dose Limiting Toxicity (DLT): DLT is defined as toxicity or events of Grade 3 or higher (80 points or higher against pain) in two or more events at the surgery site among swelling, tenderness, range of motion, and pain in any one visit. DLT is also defined as adverse drug reaction of Grade 3 or higher in the Common Toxicity Criteria Adverse Events (CTCAE), Version 4.0, with the exception of the following events and that they are unresolved for 7 consecutive days, despite medical interventions:

- ✓ Abnormal results in lab test (Acidosis, Hyponatremia, Hyperbilirubinemia, etc.)
- ✓ Fatigue, defined as not relieved by rest; limiting self-care ADL
- ✓ Pain, defined as severe pain; limiting self-care ADL
- ✓ Headache, defined as severe pain in various parts of the head, limiting self-care ADL Fever, defined as > 40.0 degrees C (> 104.0 degrees F) for > 24 hours

Maximum Tolerated Dose (MTD): If DLT occurs in 2 or fewer patients at the Dosage B level, the MTD will be Dosage B. If DLT occurs in 3 or more patients treated with Dosage B then the MTD will be Dosage A. If DLT occurs in 3 patients treated with Dosage A then the MTD will not have been determined in this study design.

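### Section 6.6 names the MTD by cohort label from a DLT count alone, so the label can cover total cell and HA exposures that no patient in this trial received

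*Combined protocol and SAP*

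**What the plan says.** The Synopsis (Study Overview) makes total exposure the quantity that is stepped up: "Patient safety will be assessed step-wise with increasing levels of total hUCB-MSC and HA exposure". Section 6.3 plans the study "for two different dose ranges", with "6-9 patients per arm depending on rate of DLT". Section 6.4 fixes one density, 0.25×10⁷ cells/cm², so each patient's total follows the size of the defect. Its chart runs from 2 to 5 cm² for A and from 6 to 9 cm² for B, and the last B row is left open upwards with a tilde.

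Section 6.5 defines B by a lower bound only: patients with lesions above 5 cm² "will be assigned to Dosage B and treated with more than" 1.25×10⁷ cells. The figure of 2.25×10⁷ appears as the top of the studied range in the Synopsis, in the primary objective (Section 5) and in Section 6.4. Eligibility does not enforce it. Inclusion criterion C in Section 6.2 ("Size of the articular cartilage lesion is") gives a minimum of 2 cm² and no maximum, and the exclusion list adds none.

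Section 6.6 then states: "If DLT occurs in 2 or fewer patients at the Dosage B level, the MTD will be Dosage B". Three or more DLTs at B make the MTD Dosage A, and three at A leave it undetermined. No readable text asks B patients to span the range or ties the MTD to the totals given. The escalation scheme in Section 6.5 is a figure that could not be read, so a restriction drawn only there cannot be excluded.

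**The concern.** In an ordinary escalation a dose level is one dose, so naming the level names the exposure that was tested. Here it does not. Density is the same in both cohorts, and the only exposure that differs between patients is the total, which the MTD rule does not use. The rule takes a cohort label and a count, and it returns the same answer whether the B defects are all just above 5 cm² or spread up to 9 cm² and beyond.

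What is at stake is the wording of the trial's dose conclusion. The report could describe as tolerated, on this trial's evidence, totals that none of its patients received, including the 2.25×10⁷ cells named in the primary objective. The planned safety summaries do not fill the gap: they are by dose cohort and pooled (Synopsis, Statistical Methods) or by dosage phase (Section 10.2.1), not by total administered.

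**Working it through.** **Inputs.** Density 0.25×10⁷ cells/cm² and volume 0.5 mL/cm² (Sections 5 and 6.4); HA 20 mg/cm² (Section 4.3); Dosage A 2–5 cm², Dosage B above 5 cm² (Sections 6.3 and 6.5); nominal top 2.25×10⁷ cells (Synopsis, Sections 5 and 6.4).

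**Step 1: reproduce the chart in Section 6.4.** Total cells = 0.25×10⁷ × defect size; HA = 20 mg × defect size.

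| Defect (cm²) | Cells (×10⁷) | HA (mg) |
|---|---|---|
| 2 | 0.5 | 40 |
| 3 | 0.75 | 60 |
| 4 | 1.0 | 80 |
| 5 | 1.25 | 100 |
| 6 | 1.5 | 120 |
| 7 | 1.75 | 140 |
| 8 | 2.0 | 160 |
| 9 | 2.25 | 180 |

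All eight rows match the plan.

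**Step 2: what each label covers.** Dosage A covers 0.5 to 1.25×10⁷ cells. Dosage B covers everything above 1.25×10⁷, nominally to 2.25×10⁷, but with no firm ceiling because the last row is open and eligibility sets no maximum size.

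**Step 3: gap between label and exposure when the MTD is Dosage B.** Let s be the largest B defect treated. The nominal top of the label divided by the largest total treated is 2.25 / (0.25 × s) = 9 / s. HA is proportional to size, so the ratio is the same for HA.

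- s just above 5 cm²: 9/5 = 1.8 (limiting value)
- s = 6 cm²: 2.25/1.5 = 1.5; in HA, 180/120 = 1.5
- s = 7 cm²: 9/7 = 1.29
- s = 8 cm²: 9/8 = 1.125
- s = 9 cm²: 1, no gap up to the nominal top

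The DLT count enters none of these lines, and s does not enter the Section 6.6 rule. Six B patients at 6 cm² or less with at most two DLTs therefore still give an MTD of Dosage B.

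**Step 4: the other branch.** Dosage A is bounded at 5 cm² but is also a range. If every A defect were 4 cm² or smaller, the label would reach 1.25/1.0 = 1.25 times the largest total treated in A.

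**Step 5: likelihood.** This needs the distribution of defect sizes among B patients. The documents do not give one, so no probability can be attached to any line of Step 3.

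**The case against.** The strongest reply is that the dose in this trial is the density, not the total. The dose rationale in Sections 6.3 and 6.4 argues that doses for local products should be expressed per unit area, because little leaves the compartment, and one density is then selected. On that reading, an MTD of Dosage B only says that this density is tolerated in defects above 5 cm².

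Other points soften the matter further. Section 6.4 reports 7 + 50 = 57 earlier Korean patients treated at the same density, up to 2.25×10⁷ total cells, with no treatment-related serious adverse event. Section 6.3 allows for a possible intermediate dose. The charter in Appendix 5 has the board review individual subject data and the draft final report. In the readable text the MTD appears only in the abbreviations and in Section 6.6; halting works directly from DLT counts (Section 6.5).

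Most of this stands and limits the importance of the point, but it does not remove it. The Synopsis itself makes total exposure the stepped quantity, and B opens only after the A cohort's 12-week DLT assessment. The Korean statement concerns serious events, whereas a DLT under Section 6.6 includes Grade 3 local findings that need not be serious. Nor does Section 6.4 say how many of those patients were near the maximum. The intermediate dose and the board's review are not tied to the MTD definition.

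**Conclusion.** The point holds as a narrow one about how the conclusion is stated. Section 6.6 turns a DLT count into a label that covers a range, and the label can extend beyond what this trial's patients received. With all B defects at 6 cm² or less the overreach is 1.5-fold in cells and HA; with one defect at 8 cm² it is 1.125-fold. These figures take 2.25×10⁷ as the nominal top and assume that the unread figure in Section 6.5 adds no restriction.

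Three stronger readings are tempting and not supported.

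- A reader might infer a safety hazard. The constant density, the earlier exposure up to 2.25×10⁷ cells and the absence of any visible use of the label to dose later patients all argue against that.
- A reader might infer that a large gap is likely. Without a defect-size distribution this cannot be said. The chance that no defect reaches 9 cm² would also be the wrong measure, since a largest defect of 8.9 cm² gives 2.225×10⁷ cells, only 1% short.
- A reader might want a rule for DLTs that cluster at the largest totals. With 6 to 9 patients per cohort there is no sound way to define one, and a listing is enough.

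Severity is minor; this is a cheap improvement.

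**What to change.** In Section 6.6, for either MTD outcome, state the MTD as the range of total cells and HA actually administered in the cleared cohort, no higher than the largest total treated. Add one listing that sets each DLT against that patient's total cells, total HA and post-debridement defect area. Give the Dosage B listing to the monitoring board with the draft final report, which Appendix 5 already requires it to review.

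The cost is two sentences and one listing. No extra patients or measurements are needed, because Section 7.2.5 already has the defect measured after debridement to calculate the dose. The downside is that the stated tolerated range may be narrower than the cohort label.

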6.7 Expected Adverse Effects and Usage Considerations

6.7.1 Expected Adverse Effects

There has not been any expected adverse effect that is directly related to the administration of CARTISTEM[®], however, mild increase in temperature, pain, nausea, and headache may occur in a response to the administration of allogenic mesenchymal stem cells. In general, adverse effects that may be observed following arthrotomy accompanied by the use of anesthesia include the followings:

- Implant site pain, pruritus, and warmth
- Nausea

CARTISTEM®

page 26 of 137

CONFIDENTIAL: These all contents herein are the sole property of MEDIPOST Co., Ltd. Any reproduction or distribution of this document without the written consent of MEDIPOST Co., Ltd is prohibited. Copyright © 2017 MEDIPOST Co., Ltd.

- Constipation
- Dyspepsia
- Headache
- Dysuria
- Dizziness
- 6.7.2 Usage Considerations
- 1) Sterility should be strictly maintained as the product involves injection into human knee joint cavity.
- 2) Should any serious adverse events occur during the administration period or within 14 days after final injection, the principal investigator must, regardless of whether or not the adverse reaction is thought to be related to the study drug, report the incident to the clinical trial review committee and MEDIPOST Co., Ltd. personnel within 24 hours of occurrence.
- 3) This drug should not be administered intravenously.
- 4) Before mixing the constituting substances of the drug, tap the vial with the fingers to make sure that the cells and the preserving solution mix properly. Do not vortex.
- 5) In order to prevent the intrusion of any foreign materials into the syringe, wipe the needle point and insertion area of the vial with ethanol before inserting the needle into the vial.

7 Investigational Product

7.1 Investigational Product

7.1.1 Trade Name

CARTISTEM[®]

7.1.2 Ingredients

- hUCB-MSCs: Human umbilical cord blood-derived mesenchymal stem cell suspension in pale pink and transparent medium

- Sodium hyaluronate: white or gray-white lyophilized sponge form

CARTISTEM®

page 27 of 137

CONFIDENTIAL: These all contents herein are the sole property of MEDIPOST Co., Ltd. Any reproduction or distribution of this document without the written consent of MEDIPOST Co., Ltd is prohibited. Copyright © 2017 MEDIPOST Co., Ltd.

7.1.3 Property

A viscous gel matrix formed by mixing umbilical cord blood-derived mesenchymal stem cell suspension and white lyophilized sodium hyaluronate

7.1.4 Storage and Handling Conditions

- Storage condition: 2 10 °C (36 50 °F)
- Shelf-life of hUCB-MSC suspension: 72 hours from the time of manufacturing
- CARTISTEM[®] after combining with sodium hyaluronate is recommended to use within 12 hours from time of the combination.

7.2 Route of Administration

7.2.1. Anesthetize a patient.

[figure not shown]
7.2.2. Gently finger-tap hUCB-MSC vial to mix and transfer 1.5 mL of the cell suspension using a sterile syringe to the HA vial. Gently mix using a sterile spatula and leave the mixture stationary until the sodium hyaluronate is completely swollen for at least 30 minutes at room temperature.

7.2.3. Perform arthroscopy to obtain more accurate measurement of the defect size.

7.2.4. Expose the cartilage defect through routine knee arthrotomy, based on defect location (medial or lateral parapatellar arthrotomy).

page 28 of 137

CONFIDENTIAL: These all contents herein are the sole property of MEDIPOST Co., Ltd. Any reproduction or distribution of this document without the written consent of MEDIPOST Co., Ltd is prohibited. Copyright © 2017 MEDIPOST Co., Ltd.

[figure not shown]

7.2.5. Debride the cartilage defect back to stable shoulders using a curet to remove any unstable or degenerated (soft and fissured) cartilage, following standard guidelines as used for microfracture or autologous chondrocyte implantation. After debridement, measure size of the defect to calculate required the dose of CARTISTEM[®].

CARTISTEM®

page 29 of 137

CONFIDENTIAL: These all contents herein are the sole property of MEDIPOST Co., Ltd. Any reproduction or distribution of this document without the written consent of MEDIPOST Co., Ltd is prohibited. Copyright © 2017 MEDIPOST Co., Ltd.

7.2.6. Create multiple holes across the entire base of the articular cartilage defect with a $2\sim3$ mm drill bit spacing the holes approximately $3\sim5$ mm apart. If active bleeding is encountered, the defect may be packed with epinephrine soaked sponges. Alternatively, thrombin (5000 Units) or thrombin spray may be used. The defect base should be without any active bleeding at the time of implantation.

- 7.2.7. Fill the holes with CARTISTEM[®] first and across the entire cartilage defect.
- 7.2.8. Deflate the tourniquet, achieve hemostasis, and close the wound.
- 7.2.9. Put a knee immobilizer and a standard cold-therapy device onto the leg of a patient.

CARTISTEM®

page 30 of 137

CONFIDENTIAL: These all contents herein are the sole property of MEDIPOST Co., Ltd. Any reproduction or distribution of this document without the written consent of MEDIPOST Co., Ltd is prohibited. Copyright © 2017 MEDIPOST Co., Ltd.

